7.2.2 Trial Flow Chart

Table 1 Trial Flow Chart

Visit number	Visit 1	Visit 2	Visit 3	Visit 4	Visit 5	Visit 6	Visit 7	Visit 8	Visit 9	Visit 10	Visit 11	Visit 12	Visit 13
	Screening	Baseline	Week 4	Week 8	Week 12	Week 16	Week 20	Week 24	4-Week Telephone F-up	12-Week F-up	24-Week F-up	36-Week F-up ^P	48-Week F-up ^P
Day		14 days after Screening	28 days after Randomisation	56 days after Randomisation	84 days after Randomisation	112 days after Randomisation	140 days after Randomisation	168 days after Randomisation	28 days after Visit 8	84 days after Visit 8	168 days after Visit 8	252 days after Visit 8	336 days after Visit 8
Window		± 7 Days	± 7 Days	± 7 Days	± 7 Days	± 7 Days	± 7 Days	± 7 Days	± 3 Days	± 14 Days	± 14 Days	± 14 Days	± 14 Days
Informed consent ^a	X												
Eligibility criteria	X	X ^b											
Demographics	X												
Medical history	X												
Prior/Concomitant medication/therapy ^c		X	X	X	X	X	X	X					
Treatment for aPAP									X	X	X	X	X
Pregnancy test and contraceptive check	X ^d	X ^d	X ^d	X ^d	X ^d	X ^d	X ^d	X ^d		X ^d	X ^d	X ^d	X ^d
Physical Exam	X		X		X			X			X		X
Vital signs	X		X		X			X			X		X
(A-a) DO ₂ , PaO ₂ ^e	X	X	X		X			X		X	X	X	X
Lung function tests ^f	X	X	X	X	X	X	X	X		X	X	X	X
6MWT ^g	X	X	X		X			X		X	X	X	X
Laboratory Safety Analyses ^h	X	X	X	X	X	X	X	X		X	X	X	X

Visit number	Visit 1	Visit 2	Visit 3	Visit 4	Visit 5	Visit 6	Visit 7	Visit 8	Visit 9	Visit 10	Visit 11	Visit 12	Visit 13
	Screening	Baseline	Week 4	Week 8	Week 12	Week 16	Week 20	Week 24	4-Week Telephone F-up	12-Week F-up	24-Week F-up	36-Week F-up ^P	48-Week F-up ^P
Day		14 days after Screening	28 days after Randomisation	56 days after Randomisation	84 days after Randomisation	112 days after Randomisation	140 days after Randomisation	168 days after Randomisation	28 days after Visit 8	84 days after Visit 8	168 days after Visit 8	252 days after Visit 8	336 days after Visit 8
Window		± 7 Days	± 7 Days	± 7 Days	± 7 Days	± 7 Days	± 7 Days	± 7 Days	± 3 Days	± 14 Days	± 14 Days	± 14 Days	± 14 Days
ECG		X			X			X			X		X
GM-CSF ⁱ		X	X										
Anti-Drug antibodies	X ^a	X ^j	X ^j		X ^j			X ^j		X ^j	X ^j		
Biomarkers ^k		X	X		X			X					
CT		X ^l						X ^l					
DSS	X							X			X		X
Dyspnoea score ^m	X	X	X		X			X		X	X	X	X
Cough scores		X	X		X			X		X	X		X
QoL score		X	X		X			X		X	X		X
Trial drug administration training	X ⁿ												
Randomisation		X											
Trial drug dosing in the clinic		X	X		X			X		X	X		
AEs		X	X	X	X	X	X	X	X	X	X	X	X
Subject Diary Card ^o		X	X	X	X	X	X	X		X	X ^q	X	X
Dispense trial drug		X	X	X	X	X	X	X		X	X ^q	X	
Compliance			X	X	X	X	X	X		X	X	X	X

- ^a Only related to anti-GM-CSF. Anti-GM-CSF blood sampling to be done during pre-screening period at trial sites that do not perform anti-GM-CSF as routine for aPAP diagnosis. Only subjects without available data will have a sample taken before screening to confirm diagnosis. Anti-GM-CSF blood sampling should be done only after collection of informed consent at such trial sites. Informed consent also to be taken in sites who conduct CT before screening.
- ^b Re-check of eligibility criteria.
- ^c Prior medication/therapy is defined as medication/therapy administered prior to first dose of trial medication. All medication/therapy administered after first dose of trial medication is considered concomitant medication/therapy.
- ^d Serum pregnancy test at Screening (Visit 1), at dosing at Baseline (Visit 2) and at all subsequent visits during trial. A urine pregnancy test will also be performed at dosing at Baseline (Visit 2) in order to immediately confirm that the subject is not pregnant and meets the inclusion criterion. Pregnancy tests (urine or serum) must continue at monthly intervals during treatment with inhaled molgramostim. Pregnancy tests at visit 10, 11, 12 and 13 for subjects who are not treated with inhaled molgramostim during the follow-up period are not mandatory.
- ^e Capillary sampling for blood gas analysis may be used instead of an arterial blood gas sample at Screening Visit 1, Visit 3, Visit 5 and all Follow-up Visits at sites that routinely use this method. Arterial sampling for blood gas is mandatory at Baseline (Visit 2) and Visit 8.
- ^f VC, DLCO, FEV₁, and FVC (all % predicted).
- ^g The need for supplemental O₂ during the procedure will be determined as part of the test at Screening or Baseline. The same O₂ flow will be used at the subsequent tests in the trial.
- ^h Haematology and clinical chemistry.
- ⁱ Samples for GM-CSF to be collected prior to 1st dose of trial drug and two hours after completion of administration of 1st dose of trial drug at Baseline (Visit 2) and prior to dosing and two hours after dosing at Week 4 (Visit 3).
- ^j Samples for anti-drug antibodies to be collected prior to administration of trial drug.
- ^k Biomarkers to be analysed: KL-6, CEA, Cyfra 21-1, SP-A, SP-B, SP-C, SP-D, and LDH.
- ^l CT can be done 4 weeks prior to the baseline visit (informed consent needs to be collected if before screening visit) and 7 days before or after Visit 8.
- ^m Dyspnoea score (BDS) to be performed before the 6MWT and also immediately after the 6MWT.
- ⁿ The subject must be trained in the inhalation and medical device maintenance procedure prior to administration of first dose of trial drug. The time and place for this training will be agreed upon at the screening visit.
- ^o Diary card to collect safety information to be given to the subject and collected at the next visit. The subject will be asked to record any AEs and answer questions regarding lung toxicity and known systemic effects in the diary card.
- ^p Visit 12 and visit 13 is only applicable to subjects who have signed the informed consent before amendment 11 to the protocol was approved by the local authorities.
- ^q Only applicable for subjects who have signed the informed consent before amendment 11 to the protocol was approved by the local authorities

7.3 Trial Period

Expected timelines:

The duration of trial participation for each subject is approximately 50 to 78 weeks:

- Screening period for the subjects is 14 days (+/- 7 days)
- Double-blind period up to 24 weeks (+/- 7 days)
- Open-label period for 24 or 48 weeks (+/- 14 days)

7.4 End of Trial

The last visit is either the 24-Week Follow-up (visit 11) or 48-Week Follow-up (Visit 13).

The end of trial is defined as the last subject's last visit (LSLV).

8 SELECTION OF TRIAL POPULATION

8.1 Number of Subjects

A total of 90 subjects are intended to be randomised. See *Section 12.2* for calculation of sample size.

8.2 Inclusion Criteria

The patients must meet all of the following criteria to be eligible to enter the trial:

- aPAP diagnosed by CT, or by biopsy, or by Broncho Alveolar Lavage (BAL), and by increased GM-CSF autoantibodies in serum
- Stable or progressive aPAP (i.e. absolute VC not improved by more than 5% and/or DLCO not improved by more than 10% - assessed from medical records) during a minimum period of two months prior to the Baseline visit
- PaO₂ <75 mmHg/<10 kPa at rest, OR desaturation of >4 percentage points on the 6MWT
- An (A-a)DO₂ of minimum 25 mmHg/3.33 kPa
- Female or male ≥18 years of age
- Females who have been post-menopausal for >1 year or females of childbearing potential after a confirmed menstrual period using a highly efficient method of contraception (i.e. a method with <1% failure rate such as combined hormonal contraception, progesterone-only hormonal contraception, intrauterine device, intrauterine hormone-releasing system, bilateral tubal occlusion, vasectomised partner, sexual abstinence), during and until 30 days after last dose of trial treatment. Females of childbearing potential must have a negative serum pregnancy test at Screening (Visit 1) and a negative urine pregnancy test at dosing at Baseline (Visit 2) and must not be lactating
- Males agreeing to use condoms during and until 30 days after last dose of trial treatment, or males having a female partner who is using adequate contraception as described above
- Willing and able to provide signed informed consent
- Willing and able to comply with scheduled visits, treatment plan, laboratory tests, and other trial procedures specified in the protocol as judged by the investigator

8.3 Exclusion Criteria

Patients meeting any of the following criteria will not be permitted to enter the trial:

- Diagnosis of hereditary or secondary PAP
- WLL within one month of Baseline
- Treatment with GM-CSF within three months of Baseline
- Treatment with rituximab within six months of Baseline
- Treatment with plasmapheresis within three months of Baseline

- Treatment with any investigational medicinal product within four weeks of Screening
- Concomitant use of sputum modifying drugs such as carbocystein or ambroxol
- History of allergic reactions to GM-CSF
- Connective tissue disease, inflammatory bowel disease or other autoimmune disorder requiring treatment associated with significant immunosuppression, e.g. more than 10 mg/day systemic prednisolone
- Previous experience of severe and unexplained side-effects during aerosol delivery of any kind of medicinal product
- History of, or present, myeloproliferative disease or leukaemia
- Known active infection (viral, bacterial, fungal or mycobacterial)
- Apparent pre-existing concurrent pulmonary fibrosis
- Any other serious medical condition which in the opinion of the investigator would make the patient unsuitable for the trial

8.4 Withdrawal of Subjects from Therapy or Assessment

8.4.1 Withdrawal from the Trial

Subjects are free to discontinue their participation in the trial at any time. Withdrawal from the trial will not affect or prejudice the subject's further care or treatment. Potential reasons for withdrawal of subjects from the trial are:

- Screening failure
- The decision of a subject to withdraw from the trial (including if the subject withdraws informed consent)
- Subject is lost to Follow-up
- Other reason(s)

The reason and date the subject is withdrawn from the trial will be documented in the electronic case report form (eCRF) (e.g. lost to Follow-up, consent withdrawn, incorrect enrolment, AEs, etc.). If a subject is withdrawn from the trial, the investigator should attempt to complete all required trial assessments (such as those at Week 24 if withdrawn during the Double-blind treatment period).

All AEs should be followed-up according to *Section 11.2*.

If a subject is withdrawn from the trial, all data collected until the time of withdrawal will be used in the analyses.

Subjects who withdraw before randomisation will be considered screen failures.

8.4.2 Discontinuation of Double-Blind Treatment

Subjects may be discontinued from double-blind treatment and assessments at any time, if deemed necessary by the investigator.

Potential reasons for discontinuation of double-blind treatment are:

- Lack of efficacy/worsening of disease
- Unacceptable AE

- Serious hypersensitivity reaction
- Pregnancy

Those who discontinue double-blind treatment will not automatically be withdrawn from the trial but will be encouraged to continue to follow the same visit schedule.

For example: if double-blind treatment is discontinued at Week 8 (Visit 4) the subject will be encouraged to attend the remaining visits in the Double-blind treatment period (Weeks 12, 16, 20 and 24) and continue into the Follow-up period. If the subject is reluctant to agree to 4-weekly visits, the investigator should request attendance at Week 24 (Visit 8) as a minimum.

The reason and date the subject is discontinued from double-blind treatment will be documented in the eCRF.

Subjects who fulfil the criteria for rescue treatment will be scheduled for a WLL as described in *Section 9.4*. Subjects receiving a WLL should continue Double-blind treatment and attend the remaining visits in the Double-blind treatment period and then continue into the Follow-up period.

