12.1.5 Primary Efficacy Analysis

The primary efficacy variable, (A-a)DO₂, will be tested using an ANCOVA model. This model will have change from baseline to Week 24 in (A-a)DO₂ as the response variable, whilst treatment group, WLL within 2 months prior to randomisation, and baseline (A-a)DO₂ will be predictor variables. The mean difference between each active dose and placebo in change from baseline of (A-a)DO₂ will be estimated, along with its 95% confidence interval (CI) and associated statistical significance test.

Subjects who withdraw from their randomised treatment before week 24 should still be followed up through to week 24. For such patients, their week 24 data will be considered as primary, irrespective of treatment discontinuation, treatment interruption(s), use of rescue

medication (WLL or other), etc. The feasibility and likely meaningfulness of this analysis will be reviewed in the blind review of the SAP, once the extent and pattern of missing data are known.

A sensitivity analysis will include a mixed model for repeated measures including factors for treatment, visit, treatment-by-visit interaction, and baseline (A-a)DO₂.

Subjects who withdraw from the study early and who do not have week 24 data available will have their (A-a)DO₂ measurement imputed using multiple imputation for which full details will be given in the Statistical Analysis Plan. Further sensitivity analyses will include:

- “reasonably worst case” scenario. For the primary analysis, patients in either of the active arms will have the value of the 10th percentile from their dose arm imputed (i.e. approximately the 3rd worst case) whilst patients in the placebo arm will have the median for the placebo arm imputed.
- Tipping point analysis: Patients in any group with a missing endpoint will be assigned progressively worse (A-a)DO₂ to find the point at which the results reverse from favouring the active treatment to the placebo.

All attempts will be made to retain subjects in the trial, even if they wish to withdraw from trial treatment. Hence it is anticipated that there will be only minimal missing (A-a)DO₂ data at week 24 and a further sensitivity analysis will use all available Week 24 data with no imputation (i.e. a “completers” analysis).

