5.3.6 Primary Efficacy analysis

The primary efficacy variable, (A-a)DO₂, will be collected at Screening, Baseline (randomisation), Week 4, 12 and 24 during treatment period, and at Week 12, 24, 36 and 48 during the follow-up period. All (A-a)DO₂ values reported in the CRF will be recalculated for statistical analyses using the equation:

$$Aa\ Gradient = \left(F_i O_2 (P_{atm} - P_{H_2O}) - \frac{P_a CO_2}{0.8} \right) - P_a O_2$$

where F_iO₂ is fraction of inspired oxygen

P_{atm} is ambient atmospheric pressure

P_{H₂O} is saturated vapour pressure of water at body temperature (set to 47 mmHg / 6.266 kPa)

P_aCO₂ is arterial partial pressure of carbon dioxide

P_aO₂ is arterial partial pressure of oxygen

Any of these assessments reported in kPa will be converted to a result in mmHg before the calculations, this will be done using a factor k=7.5.

The primary efficacy endpoint, absolute change from baseline of (A-a)DO₂ after 24-weeks treatment, will be analysed based on an ANCOVA model including treatment group, WLL (stratification), Japan vs other countries, and baseline (A-a)DO₂. The data from the three treatment groups will be analysed all together (all treatment groups included in one model). Contrasts will be set up to estimate treatment differences in change from baseline with 95% confidence intervals (CI) and the corresponding p-value for Molgramostim OD vs. Placebo and for Molgramostim intermittently vs. Placebo.

For each analysis two sided tests will be performed where the null hypothesis is that there is no difference between treatment groups, which will be tested against the alternative that

there is a difference. Control for type-1 error inflation due to multiple testing will be handled as described in section 5.4.

A de-facto estimand approach will be applied, where for the primary analysis, all observed data will be included, irrespective of subject adherence to the randomised treatment. Subjects who withdraw from their randomised treatment before week 24 will be followed up through to week 24, and their week 24 data will be considered as primary, irrespective of treatment discontinuation, treatment interruption(s), use of rescue medication (WLL or other), etc.

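### The opening sentence of protocol 8.4.2 lets the investigator end assessments along with blinded treatment, which does not fit the plan to follow subjects off treatment to Week 24

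*Protocol*

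**What the plan says.** **Protocol 8.4.2** begins: "Subjects may be discontinued from double-blind treatment and assessments at any time, if deemed necessary by the investigator". A list of possible reasons follows, but its lead-in refers to discontinuing double-blind treatment only. The section then turns towards retention. Subjects who stop drug "will not automatically be withdrawn from the trial but will be encouraged to continue to follow the same visit schedule", and if a subject is reluctant to attend every four weeks, "the investigator should request attendance at Week 24 (Visit 8) as a minimum". Subjects who have a rescue whole lung lavage (WLL) are to stay on blinded treatment and attend the remaining visits.

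**Protocol 8.4.1** deals with leaving the trial. Its bulleted reasons are screening failure, the subject's decision, loss to follow-up and an open category of other reasons. AEs and incorrect enrolment appear only among examples of what to record in the eCRF ("e.g. lost to Follow-up, consent withdrawn, incorrect enrolment, AEs, etc"). After withdrawal, "the investigator should attempt to complete all required trial assessments (such as those at Week 24 if withdrawn during the Double-blind treatment period".

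**Protocol 12.1.5** states: "Subjects who withdraw from their randomised treatment before week 24 should still be followed up through to week 24". It adds: "All attempts will be made to retain subjects in the trial, even if they wish to withdraw from trial treatment".

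**SAP 5.3.6** is firmer: "Subjects who withdraw from their randomised treatment before week 24 will be followed up through to week 24". It describes a de-facto estimand that includes all observed data whatever the adherence or rescue use.

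**The concern.** The primary analysis, and the ANCOVAs for 6MWD and SGRQ total score, follow a treatment-policy idea: what counts is the Week 24 value, on or off drug. That works only if stopping drug and stopping assessments are kept apart. The first sentence of 8.4.2 joins them and leaves the decision to the investigator.

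If the permission is used, the subjects affected are unlikely to be a random sample. An investigator who judges it necessary to stop is reacting to how the subject is doing. The missing Week 24 values could then depend on the values themselves, and an analysis of observed values would be biased. At stake are the primary endpoint and two of the three key secondary endpoints in the confirmatory testing sequence.

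**Working it through.** **1. The passages side by side.**

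| Place | What happens to assessments when drug stops |
|---|---|
| Protocol 8.4.2, first sentence | may be ended by the investigator |
| Protocol 8.4.2, later text | continuation encouraged; Week 24 requested as a minimum |
| Protocol 12.1.5 | should continue to Week 24 |
| SAP 5.3.6 | will continue to Week 24 |

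The first row does not fit the other three. The later text of 8.4.2 deals with a reluctant subject; it does not limit an investigator who relies on the first sentence.

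**2. What happens to a subject whose assessments are ended early.**
- An assessment done at withdrawal and entered on the Week 24 page is moved to the visit nearest withdrawal (SAP 5.3.1). It does not serve as a Week 24 value.
- The main ANCOVA uses observed data (SAP 5.3.6). Multiple imputation, which protocol 12.1.5 specifies for missing Week 24 values, is listed in the SAP as a sensitivity analysis. The subject drops out of the main test.
- For (A-a)DO₂, the SAP adds a tipping-point analysis (only if superiority has been shown) and a reasonable-worst-case analysis. For 6MWD and SGRQ, SAP 5.3.7 limits the sensitivity analyses to MMRM, multiple imputation, completers and per-protocol. None of these four explores values missing because they were poor.

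**3. Reproducing the plan's own figures.** Two-sample t-test, noncentrality = δ / (SD × √(1/n₁ + 1/n₂)).
- Primary (protocol 12.2, Table 3): δ = 10, SD = 7.5, two-sided α = 0.01, n = 14 and 28. Noncentrality = 10 / (7.5 × √(1/14 + 1/28)) = 4.07 on 40 df; power 0.908. With 13 and 26, power is 0.879. The stated total of 42 reproduces.
- 6MWD (SAP Appendix 2): δ = 50, SD = 70.2, α = 0.05, 43 per group; power 0.904. It reproduces.
- SGRQ (SAP Appendix 2): δ = 10, SD = 10.1, α = 0.05, 23 per group; power 0.908. It reproduces.

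**4. Loss of power.** The documents give no dropout rate, so 0, 5, 10, 15 and 20% missing from 45 per arm is an assumed range (45, 42, 40, 38 and 36 observed).
- Primary, pairwise, δ = 10, SD = 7.5, α = 0.05: power stays above 0.999 throughout.
- 6MWD, δ = 50, SD = 70.2, unadjusted α = 0.05: 0.916, 0.897, 0.882, 0.865, 0.846.

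For the primary endpoint the issue is therefore bias, not power.

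**5. Upper bound on the bias for a given number lost.** If the worst fraction p of a normal sample is removed, the mean of the rest shifts by SD × φ(z) / (1 − p), where z is the upper-p normal quantile. Inputs: 45 per arm (SAP 3.2); SDs and planning differences as in step 3. The numbers lost (2 or 4, all in one arm) are assumptions.
- p = 2/45 = 0.0444: z = 1.701, φ(z) = 0.0938, factor = 0.0938 / 0.9556 = 0.0982.
- p = 4/45 = 0.0889: z = 1.348, φ(z) = 0.1609, factor = 0.1609 / 0.9111 = 0.1766.

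| Endpoint | SD | Worst 2 lost | Worst 4 lost | Share of planning difference |
|---|---|---|---|---|
| (A-a)DO₂ | 7.5 mmHg | 0.74 | 1.32 | 7% to 13% of 10 |
| 6MWD | 70.2 m | 6.9 | 12.4 | 14% to 25% of 50 |
| SGRQ | 10.1 points | 1.0 | 1.8 | 10% to 18% of 10 |

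Losses on active flatter active; losses on placebo flatter placebo.

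**The case against.** The strongest reply is that one loose clause is being read against the whole of the section around it. Much of that reply stands.

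- A reader might infer that 8.4.2 names worsening or AEs as grounds for ending assessments. It does not: those reasons are given for stopping treatment.
- A reader might infer that 8.4.1 makes AEs and incorrect enrolment criteria for leaving the trial. They are only examples of reasons to record, and the same section asks for Week 24 assessments even after withdrawal.
- A reader might infer that the protocol contradicts an analysis that needs everyone's Week 24 value. Neither document requires that. Both provide for missing values, and 12.1.5 commits to retention and expects little missing data.
- The shifts in the table assume that exactly the worst values go missing, in one arm only. No document suggests that this will happen, and losses on placebo would work against the drug.
- Whether imputation belongs in the main analysis is a separate question, which editing 8.4.2 will not settle.
- A flat rule that assessments end only on withdrawal of consent, loss to follow-up or death would ignore safety. Week 24 includes a CT scan and a mandatory arterial sample, and pregnancy is a listed reason for stopping drug. Deleting AEs as a recordable reason would also lose information on why data are missing.

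The reply does not dispose of the first sentence itself. It gives a permission that the rest of the plan assumes nobody has, and using it removes the subject from the main test.

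**Conclusion.** The point holds as an inconsistency in wording with a possible effect on bias. The investigator's discretion to end assessments does not fit the later text of 8.4.2, protocol 12.1.5 or SAP 5.3.6. Under the SAP's handling of observed data and early-termination visits, using it would take subjects out of the main analyses of (A-a)DO₂, 6MWD and SGRQ.

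The size cannot be known from the documents. The (A-a)DO₂ shifts of about 0.7 and 1.3 mmHg are upper bounds for 2 and 4 subjects lost from one arm of 45. They rest on a normal distribution, the planning SD of 7.5 and an unadjusted arm mean. The direction depends on which arm loses subjects. Nothing here invalidates the primary analysis, but the sentence is worth correcting because the remedy is cheap.

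**What to change.** 1. In protocol 8.4.2, delete *and assessments* from the first sentence.
2. Add that stopping blinded treatment for any reason, including an AE, worsening or ineligibility found after randomisation, is recorded as treatment discontinuation and does not by itself end trial participation.
3. State that the Week 24 primary and key secondary assessments are still sought at the scheduled time unless the subject withdraws consent, is lost to follow-up or dies, and that the investigator may omit an individual procedure for safety.
4. In 8.4.1, keep AEs and incorrect enrolment as recordable reasons, but make clear that they are not in themselves grounds for ending follow-up of a randomised subject.

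The rules for stopping treatment are unchanged. The cost is a wording change, a reminder to sites and a few more off-drug visits, which the protocol already requests.
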